- Desire for opioids: A single item, “Did you experience craving for opioids at any point this week?”, anchored on a 10-point scale (0=Not at all; 10=Extremely).
- Mood: Affect will be assessed by representative items from the Positive-Negative Affect Scale (PANAS), adapted to a weekly time orientation.
- Stress will be assessed by a single item “How would you rate your overall level of stress this week?”, anchored on a 7-point scale (No Stress – Worst possible stress)
- Mindfulness. Three mindfulness constructs will be assessed with items from the Awareness (2 items) and Non-Reactivity (2 items) subscales of the Five Factor Mindfulness Questionnaire, and from the Acceptance and Action Questionnaire (2 items).

Activities to meet Aim 3 (Exploratory). A focused implementation evaluation will be conducted with the goal of informing actionable strategies to promote sustainability of MMORE after the NH STR funding has ended. We will use mixed methods to evaluate implementation of MMORE and will draw from implementation science frameworks to guide evaluation. We will use implementation metrics as well as surveys and interviews with participants and obstetric practice stakeholders to evaluate implementation.

At the end of each virtual 8-session intervention period, MMORE participants will complete a Satisfaction Survey regarding their experience (1 to 7 response scale), including: how much liked the intervention, how much the intervention improved awareness of stress and craving triggers, perceived level of confidence to use strategies for awareness, use of acceptance and non-judgment when experienced stress, negative affect and cravings, extent to which intervention helped participant think about their coping strategies and sources of support related to parenting, and likelihood of recommending the intervention to a friend.

We will use the Consolidated Framework for Implementation Research (CFIR) as a conceptual model to guide assessment of barriers and facilitators to implementation and sustainability of MMORE. Interview guides will be constructed with items from the CFIR repository (www.cfir.org) used in other studies. Interviews will tap perspectives related to the intervention itself, attitudes of women with OUD and obstetric and MOUD provider stakeholders about the yoga-mindfulness approaches, and federal and NH state policies (i.e., reimbursement, NH STR initiative) that could support or impede continued offering of the intervention.

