Aim 2: For examining mediation/mechanistic effects at the individual-level from longitudinal data via parallel process growth models (paths from treatment assignment to individual-level slope of mediator to individual-level slope of outcome), with 120 individuals, there will be 80% power to detect indirect effects comprised of a small-medium effects of the intervention arm on latent slope of mindfulness (defined as a correlation of 0.25 between variables or equivalently as explaining 6% of the variance in the latent mindfulness slope) and a medium effect of the slope of mindfulness on the slope of the outcome (defined as a correlation of 0.36 or equivalently as explaining 13% of the variance of the outcome). For examining mediation/mechanistic effects at the weekly level, power is less clear. Although DSEM combines aspects of more familiar modeling techniques, it is new and thus limited information is available on determining power for such models. In one set of simulation studies, good model performance was observed for several models differing in complexity for a sample size of 200 individuals with a number of observations per individual ranging from 20-200, and good model performance for all but the most complex models for smaller sample sizes. Thus, with data from 120 individuals contributing up to 8 observations each, we expect to have enough data to accomplish the aim of understanding the mechanisms underlying the intervention effects of MMORE. We will conduct weekly assessments to minimize participant burden. This strategy will still allow us adequate sampling frequency to track changes in outcome measures over the course of treatment. The power

calculations for the mechanistic effects were based on individual-level latent slope variable estimates and are thus not affected by a change to the number of indicator variables for the latent slope variables (reduced from 70 daily assessments to 8 weekly assessments). Power calculations for the dynamic SEM models are approximate and were not specifically based on having daily assessments per individual so will also not change.

Aim 3 is exploratory and not powered.

Treatment Assignment Procedures

Randomization will be conducted via permuted blocks. Once 8-10 participants have enrolled, an intervention will commence for that cohort. The randomization block size would be random, with blocks of size 4, 6, and 8. We plan ongoing recruitment and to start a new group approximately every 8 weeks.

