framework that allows for estimating simultaneous sets of equations involving latent and observed variables, thus allowing modeling of multi-level data, and modeling relationships at each level including mediation. Unlike non-dynamic SEM, however, DSEM have the capability to estimate time-series model(s) at the within-individual level, and also allow for a between-time level model (in addition to the between-individual level model) to incorporate time-varying effects observed in intensively collected data (i.e. creating a cross-classified model). Thus DSEM combine the advantages of time-series models, multi-level models, time-varying effect models, and other SEM, and importantly for the current application allows examination of relationships between multiple intensively collected variables (here affective state, mindfulness, stress, and craving) as well as moderation of these relationships by both individual-level (here treatment arm) and daily-level (session attendance, mindfulness) variables. The DSEM is specified by models at three levels. The three-level specification results from a decomposition of the observed variable(s) for a given individual at a given time (vector Y_{it}^*) into three latent, unobserved parts: an individual-specific contribution $Y_{2,i}$ a time-specific contribution $Y_{3,t}$ and a deviation for an individual, at a given time $Y_{1,it}$ ($Y_{it}^* = Y_{1,it} + Y_{2,i} + Y_{3,t}$). For example, for stress, observed weekly stress ($dStr_{it}^*$), becomes: $dStr_{it}^* = dStr_{it} + Str_i + Str_t$. These three latent components are then modeled simultaneously in a within-individual, between-individual, and between-time model. The time series describing the relationship between past and current observations in one or more intensively collected variables is modeled at the within-individual level (detailed below) The between-individual model examines influences on mean weekly stress (Str_i) and mean weekly craving as well as influences on individual-level random effects specified in the within-individual model (e.g. $\varphi_{SC,i}$: representing the relationship between weekly craving and weekly stress). The between-time model examines influences on the mean daily stress at a given time (Str_t) and on mean weekly craving at a given time (as well as influences on time-specific random effects specified at the within-individual model). For the current application, one within-individual model is a bivariate autoregressive (here specified with a lag of 1 but other lags will be explored) of weekly stress ($dStr_{it}$) and weekly craving (dCr_{it}).

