
$$\begin{aligned} dStr_{it} &= \varphi_{SS,i} dStr_{it-1} + \varphi_{SC,i} dCr_{it-1} + \zeta_{S,it} \\ dCr_{it} &= \varphi_{CC,i} dCr_{it-1} + \varphi_{CS,i} dStr_{it-1} + \zeta_{C,it} \end{aligned}$$

We will obtain an estimate of the relationship between the current value of dCr and lagged value(s) of dStr ($\varphi_{CS,i}$). Moderation of this relationship by immediate contextual variables (such as weekly mindfulness value, mindfulness session attendance (among those on MMORE arm)) can be examined by including an interaction between time-varying context variables and dCr in the dStr equation. Since the regression parameters estimated are considered random individual effects, associations with other individual-level variables (such as treatment arm assignment) can be modeled in the between-individual model. This will allow us to examine moderation of the weekly relationship between dStr and dCr by individual-level variables. Mediation of the effect of immediate contextual variables on mRB by mSR will be evaluated using a cross-lagged mediation model.

Aim 3 (Exploratory). Quantitative data will be descriptively summarized, and qualitative data coded for salient themes using standard deductive methods described earlier. Data summaries will be reviewed by the Steering Committee and consultants to inform strategies to support dissemination and sustainable implementation of MMORE in women's health care settings. Data will guide interpretation of participant outcomes.

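### Aim 2 names lagged stress to craving as the path to be moderated but puts the interaction in the stress equation, so that moderation is not tested; the claim that weekly data leave mediation power unchanged is also unsupported

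*Combined protocol and SAP*

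**What the plan says.** **Moderation (section 9.6, Aim 2).** Two lag-1 equations are displayed. In the dStr (weekly stress) equation, lagged craving has coefficient φ_SC. In the dCr (weekly craving) equation, lagged stress has coefficient φ_CS. The text says that the plan will estimate the "relationship between the current value of dCr and lagged value(s) of dStr", labelled φ_CS, and that moderation of this relationship by context (weekly mindfulness, session attendance) can be examined by "including an interaction between time-varying context variables and dCr in the dStr equation". Just before the equations, φ_SC is given as an example of a random effect, "representing the relationship between weekly craving and weekly stress". The model is introduced as "one within-individual model is a bivariate autoregressive", but no other is written out. The same paragraph ends: "Mediation of the effect of immediate contextual variables on mRB by mSR will be evaluated using a cross-lagged mediation model". Neither mRB nor mSR is defined anywhere in the document.

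**Power (section 9.2, Aim 2).** With 120 individuals, 80% power is stated for an indirect effect through the latent slope of mindfulness, with correlations of 0.25 (arm to mindfulness slope) and 0.36 (mindfulness slope to outcome slope). The calculations are described as "thus not affected by a change to the number of indicator variables for the latent slope variables". The change meant here is the move from a daily to a weekly schedule, with the count "reduced from 70 daily assessments to 8 weekly assessments". For the dynamic models the section gives no power figure and calls the position unclear. It cites simulations with 20 to 200 observations per person, and concludes that up to 8 per person should be enough.

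**The concern.** An analyst who programs the contextual moderation as written would fit a term in an equation that does not contain the named path. If the term uses lagged craving, a significant result would describe craving leading to later stress while being reported as stress leading to later craving. A null result would say nothing about the stated question. The undefined symbols leave the weekly mediation model without named variables.

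The power statement matters for interpretation. A null mediation result for a mindfulness pair that uses weekly data would be read against an 80% figure whose dependence on slope precision is not stated. Aim 1, the sample size and data collection are not touched.

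**Working it through.** **1. Target against term.** From the displayed equations in section 9.6:

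- dStr(t) = φ_SS·dStr(t−1) + φ_SC·dCr(t−1) + error
- dCr(t) = φ_CC·dCr(t−1) + φ_CS·dStr(t−1) + error

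Add γ·context·dCr(t−1) to the dStr equation, and the slope of lagged craving becomes φ_SC + γ·context. φ_CS does not appear. If dCr is read without a lag, as literally written, the term multiplies a variable that has no coefficient in the displayed dStr equation, so it moderates no displayed path. Moderation of φ_CS needs context × dStr(t−1) in the dCr equation.

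A simulation illustrates this (1,500 runs, 120 people, 8 weeks, pooled regression). The assumed values are autoregression 0.3, φ_SC 0.15, φ_CS 0.25 and true moderation of φ_CS of −0.10. The term as written, with lagged craving, averaged −0.001 and was significant in 3.9% of runs, about the null rate. The matching term in the dCr equation averaged −0.101 and was significant in 87%.

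**2. Reproducing the 80%.** Inputs from section 9.2: n = 120, a = 0.25, b = 0.36. Assumed: no direct effect, two-sided 5%, slopes without error. Joint test with noncentral t, noncentrality r/√(1−r²)·√120:

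- a path: 0.25/√0.9375 × 10.954 = 2.83, df 118, power 0.801.
- b path: partial correlation given arm = 0.36(1−0.0625)/√(0.9375 × 0.9919) = 0.350; noncentrality 4.09, df 117, power 0.982.
- Product: 0.801 × 0.982 = 0.787.

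Simulated percentile bootstrap: 78% to 79%. The stated figure is therefore recovered with error-free slopes. A bias-corrected bootstrap gives 83% to 84%.

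**3. Adding slope error.** No slope reliability is given, so values are assumed. With error in the mediator slope only, its correlations are multiplied by √R: joint power is 76% at R = 0.95, 73% at 0.9 and 66% at 0.8. This regression on error-contaminated slopes approximates the planned latent growth model.

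**4. Effect of the schedule change.** Slope error variance is report error variance divided by the sum of squared times (weeks²). This is 583.2 for 70 daily reports, 42.0 for 8 consecutive weekly reports and 83.3 for 8 reports over the full 70-day span. If a weekly report is as precise as a 7-day mean:

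- same span: 583.2/(7 × 83.3) = 1.0, no loss;
- 8-week span: 583.2/(7 × 42.0) = 2.0, error variance doubles.

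After doubling, R1 = R0/(R0 + 2(1−R0)). If 0.25 and 0.36 refer to true slopes, power is taken at R1. If they refer to slopes as estimated daily, reliability is already inside them and only R1/R0 applies.

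| Daily R0 | R1 | True-slope reading: before → after | R1/R0 | Estimated-slope reading: before → after |
|---|---|---|---|---|
| 0.95 | 0.905 | 76% → 73% | 0.952 | 79% → 76% |
| 0.90 | 0.818 | 73% → 68% | 0.909 | 79% → 74% |
| 0.80 | 0.667 | 66% → 55% | 0.833 | 79% → 69% |

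**5. Dynamic models.** At most 8 observations per person, against a cited minimum of 20.

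**The case against.** **On the equation.** The wording is permissive, the model is introduced as one example, and other lags are to be explored, so this may be a drafting slip that a programmer would correct. That limits the consequence but does not settle which way to correct it: the target sentence names φ_CS, while the earlier example uses φ_SC. A reader might infer that all Aim 2 moderation is misdirected, or that a significant result must describe craving leading to later stress. Neither follows. Moderation by arm is modelled through the individual random effects and is untouched, and the reverse-path interpretation requires lagged craving, which the text does not specify.

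**On power.** The 80% reproduces, and section 9.2 can be read as referring to estimated slopes, in which case reliability is already inside 0.25 and 0.36. A bias-corrected bootstrap still reaches 80% at mediator reliability 0.9, and section 9.6 does not state the bootstrap type. The weekly items ask about the whole week ("How would you rate your overall level of stress this week"), so treating a weekly report as no better than a single daily one would be harsh. All of this stands. A reader might infer that the 80% is wrong, or that the weekly schedule has left Aim 2 underpowered; the documents support neither. What survives is narrower: on the true-slope reading the calculation has no term for precision and cannot show that power is unchanged, and on the estimated-slope reading the correlations themselves can change with the schedule.

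**On the dynamic models.** Section 9.2 already admits that this power is unclear and approximate. Only its closing inference is at issue.

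**Conclusion.** The main point holds on the text alone, without assumptions: the contextual moderation specified in section 9.6 does not test the path it names, and the weekly mediation sentence uses undefined variables.

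The power point is secondary. The claim that power is unaffected by the schedule is unsupported on either reading, but the size of any loss is unknown. It is zero at equal precision over the same span. Under an assumed doubling of error variance, power is 73%, 68% or 55% on the true-slope reading and 76%, 74% or 69% on the estimated-slope reading, for assumed daily reliabilities of 0.95, 0.9 and 0.8. These figures rest on mediator error only, a joint test and a regression approximation.

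The point applies only to mindfulness pairs that use weekly data, because the 80% is stated only for a mindfulness-slope mediator. Mindfulness-craving must use weekly data, since section 6.1 lists craving only there. For mindfulness-retention and mindfulness-pain, section 9.6 does not say whether the weekly items or the three-wave scale will be used.

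The dynamic-model point is minor. One might conclude that 8 occasions are too few, but the document shows only that its cited range does not reach 8; whether the smaller samples it mentions include fewer occasions is not stated.

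**What to change.** **Section 9.6.** Confirm the target path and make the target sentence and the term agree. If it is φ_CS, as the target sentence states: *Moderation of φ_CS will be tested by context × lagged dStr in the dCr equation.* If it is φ_SC, as in the earlier example, correct the target sentence and write the term with lagged dCr. Replace mRB and mSR with the intended weekly variables.

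**Section 9.2.** Delete the statement that mediation power does not depend on the number of assessments. Restate the 80% as conditional on a stated slope reliability and bootstrap type, checked by a short simulation at 8 occasions with the week span given, and name the mindfulness pairs that use weekly data. Replace the assurance about the dynamic models with a statement that the cited range does not cover 8 occasions and that adequacy at 8 is not established in this document.

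**Cost.** SAP wording and a short simulation. The stated Aim 2 power becomes conditional and may look less favourable. Data collection, sample size and Aim 1 do not change. The path should be settled before analysis, so that it is not chosen after results are seen.

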10. DATA COLLECTION AND QUALITY ASSURANCE

10.1 Data Collection Forms

Opioid abstinence and MOUD treatment retention will be collected by way of medical chart data extraction and self-report by consented participants.

Secondary outcomes will be collected by way of self-report by consented participants through completion of assessment surveys.

Case Report data collection forms have been created for the following:

- Participant Demographics and physical conditions at baseline
- Session Events Form
- Intervention Experience Form
- Weekly Monitoring Form
- Adverse Events
- Clinical Record Data Collection Template
- Self-Report Assessment Battery (SRAB)

The SRAB has been programmed in secured, password protected HIPAA compliant online survey software (Dartmouth College REDCap). Individual participant survey links will correspond to the unique participant study ID so that all pages of each assessment survey (and corresponding database) will be linked to the participant.

10.2 Data Management

Participant data will be coded with unique study identifier numbers with all identifying information removed. Any paper-version surveys will be entered into the secured online system and stored in locked filing cabinets, in locked offices at the Center for Technology and Behavioral Health (CTBH). All data collected on mobile tablets or laptops will be done so via secured online surveys accessed through password-protected links, and data will be stored in secured databases on secure cloud-based servers. The lead project coordinator will have the primary responsibility for securely storing any audio recordings of interviews completed as a part of this study. Recordings, participant data, and de-identified transcripts of interviews will be stored on the research study staff secure and password-protected computers and destroyed after study completion.

10.3 Quality Assurance

10.3.1 Training

Lead Yoga Practitioner [name] will train two other highly experienced yoga instructors in the Mindful Moms intervention using the training materials and manual developed in first year of the project.

10.3.2 Quality Control Committee

We have identified three independent monitors for the R33 study and their materials have been provided to the study Project Official.

10.3.3 Metrics

Intervention sessions will be video and audio recorded to allow for evaluation of fidelity over the

course of the study.

The study team will review data weekly to ensure quality and completeness.

The study data engineer will develop and maintain the database and prepare the dataset for analyses.

10.3.4 Protocol Deviations

All intervention protocol deviations will be clearly denoted on the *Session Events Form*.

All research study protocol deviations will be clearly denoted on *Protocol Deviations Form*.

10.3.5 Monitoring

Data accuracy and completeness will be monitored by the lead project coordinator.

The Independent Monitors will also receive quarterly summaries of study progress, recruitment and retention indices, and any adverse events.

11. PARTICIPANT RIGHTS AND CONFIDENTIALITY

11.1 Institutional Review Board (IRB) Review

This protocol and associated documentation has been submitted to the Dartmouth College Institutional Review Board for approval.

11.2 Informed Consent Forms

We adapted the IRB-approved consent form for the R21 Pilot Study for use in the R33 phase study. The consent forms describe the overall nature of the study, the potential risks and benefits, and the study activities and incentives for participants.

11.3 Participant Confidentiality

A Certificate of Confidentiality has been obtained for this protocol.

All efforts will also be made to protect confidentiality in the context of the Mindful Moms Intervention sessions. Only first names will be used. Participant access to the mobile prototype components of the intervention and online assessment surveys will require unique user login and password, and loss of passwords will require double authentication. Assessment data will be encrypted and secured thus mitigating or reducing the risk of data loss during the transmission process. All study assessments will be coded with a unique study ID. We will not collect personally identifiable information in the research database.

All data collected will be housed on a secure, encrypted cloud server. Data will be collected using current state-of-the-field Transport Layer Security (TLS) encryption to prevent eavesdropping and tampering of data while it is in the transmission pipeline. All assessment data will be stored in secure, password protected databases that will not be directly linked to participant identifying information. A separate, secure database of study participants contact information will be created to maximize security. All paper documentation will be kept in locked file cabinets located in a locked study team office. All possible safeguards will be taken to prevent disclosure of personal information, including during any communication with participants (we will NOT use text messages to participants). Participants will be instructed not to share their mobile phones.

Confidentiality training will be required for all new employees and project members and refresher

seminars will be offered annually for all employees. All research staff will fulfill the educational requirements set forth by the Office for Human Research Protections at Dartmouth College. Data for all participants will be kept strictly confidential, except as mandated by law. All data will be presented in de-identified, aggregate formats.

